11.1.1 Definitions

Evaluable for Target Disease response. Only those participants who have measurable disease present at baseline, have received at least one cycle of therapy, and have had their disease re-evaluated will be considered evaluable for target disease response. These participants will have their response classified according to the definitions stated below. (Note: Participants who exhibit objective disease progression prior to the end of cycle 1 will also be considered evaluable.)

Evaluable Non-Target Disease Response. Participants who have lesions present at baseline that are evaluable but do not meet the definitions of measurable disease, have received at least one cycle of therapy, and have had their disease re-evaluated will be considered evaluable for non-target disease. The response assessment is based on the presence, absence, or unequivocal progression of the lesions.

11.1.2 Disease Parameters

Measurable disease. Measurable lesions are defined as those that can be accurately measured in at least one dimension (longest diameter to be recorded) as ≥ 20 mm by chest x-ray or ≥ 10 mm with CT scan, MRI, or calipers by clinical exam. All tumor measurements must be recorded in millimeters (or decimal fractions of centimeters).

Malignant lymph nodes. To be considered pathologically enlarged and measurable, a lymph node must be ≥ 15 mm in short axis when assessed by CT scan (CT scan slice thickness recommended to be no greater than 5 mm). At baseline and in follow-up, only the short axis will be measured and followed.

Non-measurable disease. All other lesions (or sites of disease), including small lesions (longest diameter < 10 mm or pathological lymph nodes with ≥ 10 to < 15 mm short axis), are considered non-measurable disease. Bone lesions, leptomeningeal disease, ascites, pleural/pericardial effusions, lymphangitis cutis/pulmonitis, inflammatory breast disease,

abdominal masses (not followed by CT or MRI), and cystic lesions are all considered non-measurable.

Note: Cystic lesions that meet the criteria for radiographically defined simple cysts should not be considered as malignant lesions (neither measurable nor non-measurable) since they are, by definition, simple cysts.

'Cystic lesions' thought to represent cystic metastases can be considered as measurable lesions, if they meet the definition of measurability described above. However, if non-cystic lesions are present in the same participant, these are preferred for selection as target lesions.

Target lesions. All measurable lesions up to a maximum of 2 lesions per organ and 5 lesions in total, representative of all involved organs, should be identified as **target lesions** and recorded and measured at baseline. Target lesions should be selected on the basis of their size (lesions with the longest diameter), be representative of all involved organs, but in addition should be those that lend themselves to reproducible repeated measurements. It may be the case that, on occasion, the largest lesion does not lend itself to reproducible measurement in which circumstance the next largest lesion which can be measured reproducibly should be selected. A sum of the diameters (longest for non-nodal lesions, short axis for nodal lesions) for all target lesions will be calculated and reported as the baseline sum diameters. If lymph nodes are to be included in the sum, then only the short axis is added into the sum. The baseline sum diameters will be used as reference to further characterize any objective tumor regression in the measurable dimension of the disease.

Non-target lesions. All other lesions (or sites of disease) including any measurable lesions over and above the 5 target lesions should be identified as **non-target lesions** and should also be recorded at baseline. Measurements of these lesions are not required, but the presence, absence, or in rare cases unequivocal progression of each should be noted throughout follow up.

11.1.3 Methods for Evaluation of Disease

All measurements should be taken and recorded in metric notation using a ruler, calipers, or a digital measurement tool. All baseline evaluations should be performed as closely as possible to the beginning of treatment and never more than 4 weeks before the beginning of the treatment.

The same method of assessment and the same technique should be used to characterize each identified and reported lesion at baseline and during follow-up. Imaging-based evaluation is preferred to evaluation by clinical examination unless the lesion(s) being followed cannot be imaged but are assessable by clinical exam.

Clinical lesions. Clinical lesions will only be considered measurable when they are superficial (*e.g.*, skin nodules and palpable lymph nodes) and ≥ 10 mm in diameter as

assessed using calipers (*e.g.*, skin nodules). In the case of skin lesions, documentation by color photography, including a ruler to estimate the size of the lesion, is recommended.

Conventional CT and MRI. This guideline has defined measurability of lesions on CT scan based on the assumption that CT thickness is 5mm or less. If CT scans have slice thickness greater than 5 mm, the minimum size of a measurable lesion should be twice the slice thickness. MRI is also acceptable in certain situations (*e.g.* for body scans).

Use of MRI remains a complex issue. MRI has excellent contrast, spatial, and temporal resolution; however, there are many image acquisition variables involved in MRI, which greatly impact image quality, lesion conspicuity, and measurement. Furthermore, the availability of MRI is variable globally. As with CT, if an MRI is performed, the technical specifications of the scanning sequences used should be optimized for the evaluation of the type and site of disease. Furthermore, as with CT, the modality used at follow-up should be the same as was used at baseline and the lesions should be measured/assessed on the same pulse sequence. It is beyond the scope of the RECIST guidelines to prescribe specific MRI pulse sequence parameters for all scanners, body parts, and diseases. Ideally, the same type of scanner should be used and the image acquisition protocol should be followed as closely as possible to prior scans. Body scans should be performed with breath-hold scanning techniques, if possible.

11.1.4 Response Criteria

11.1.4.1 Evaluation of Target Lesions

Complete Response (CR): Disappearance of all target lesions. Any pathological lymph nodes (whether target or non-target) must have reduction in short axis to <10 mm.

Partial Response (PR): At least a 30% decrease in the sum of the diameters of target lesions, taking as reference the baseline sum diameters.

Progressive Disease (PD): At least a 20% increase in the sum of the diameters of target lesions, taking as reference the smallest sum on study (this includes the baseline sum if that is the smallest on study). In addition to the relative increase of 20%, the sum must also demonstrate an absolute increase of at least 5 mm. (Note: the appearance of one or more new lesions is also considered progressions).

Stable Disease (SD): Neither sufficient shrinkage to qualify for PR nor sufficient increase to qualify for PD, taking as reference the smallest sum diameters while on study.

11.1.4.2 Evaluation of Non-Target Lesions

Complete Response (CR): Disappearance of all non-target lesions and normalization of tumor marker level. All lymph nodes must be non-pathological in size (<10 mm

short axis).

Note: If tumor markers are initially above the upper normal limit, they must normalize for a patient to be considered in complete clinical response.

Non-CR/Non-PD: Persistence of one or more non-target lesion(s) and/or maintenance of tumor marker level above the normal limits.

Progressive Disease (PD): Appearance of one or more new lesions and/or *unequivocal progression* of existing non-target lesions. *Unequivocal progression* should not normally trump target lesion status. It must be representative of overall disease status change, not a single lesion increase.

Although a clear progression of “non-target” lesions only is exceptional, the opinion of the treating physician should prevail in such circumstances, and the progression status should be confirmed at a later time by the review panel (or Principal Investigator).

11.1.4.3 Evaluation of New Lesions

The finding of a new lesion should be unequivocal (i.e. not due to difference in scanning technique, imaging modality, or findings thought to represent something other than tumor (for example, some ‘new’ bone lesions may be simply healing or flare of pre-existing lesions). However, a lesion identified on a follow-up scan in an anatomical location that was not scanned at baseline is considered new and will indicate PD. If a new lesion is equivocal (because of small size etc.), follow-up evaluation will clarify if it truly represents new disease and if PD is confirmed, progression should be declared using the date of the initial scan on which the lesion was discovered.

11.1.4.4 Evaluation of Best Overall Response

The best overall response is the best response recorded from the start of the treatment until disease progression/recurrence (taking as reference for progressive disease the smallest measurements recorded since the treatment started). The patient's best response assignment will depend on the achievement of both measurement and confirmation criteria.

For Participants with Measurable Disease (i.e., Target Disease)

Target Lesions	Non-Target Lesions	New Lesions	Overall Response	Best Overall Response when Confirmation is Required*
CR	CR	No	CR	>4 wks Confirmation**
CR	Non-CR/Non-PD	No	PR	≥4 wks Confirmation**
CR	Not evaluated	No	PR	

PR	Non-CR/Non-PD/not evaluated	No	PR	
SD	Non-CR/Non-PD/not evaluated	No	SD	Documented at least once ≥ 4 wks from baseline**
PD	Any	Yes or No	PD	no prior SD, PR or CR
Any	PD***	Yes or No	PD	
Any	Any	Yes	PD	

* See RECIST 1.1 manuscript for further details on what is evidence of a new lesion. ** Only for non-randomized trials with response as primary endpoint. *** In exceptional circumstances, unequivocal progression in non-target lesions may be accepted as disease progression.
 
Note: Participants with a global deterioration of health status requiring discontinuation of treatment without objective evidence of disease progression at that time should be reported as “symptomatic deterioration.” Every effort should be made to document the objective progression even after discontinuation of treatment.
				

For Participants with Non-Measurable Disease (i.e., Non-Target Disease)

Non-Target Lesions	New Lesions	Overall Response
CR	No	CR
Non-CR/non-PD	No	Non-CR/non-PD*
Not all evaluated	No	not evaluated
Unequivocal PD	Yes or No	PD
Any	Yes	PD

* ‘Non-CR/non-PD’ is preferred over ‘stable disease’ for non-target disease since SD is increasingly used as an endpoint for assessment of efficacy in some trials so to assign this category when no lesions can be measured is not advised
		

11.1.5 Duration of Response

Duration of overall response: The duration of overall response is measured from the time measurement criteria are met for CR or PR (whichever is first recorded) until the first date that recurrent or progressive disease is objectively documented (taking as reference for progressive disease the smallest measurements recorded since the treatment started, or death due to any cause. Participants without events reported are censored at the last disease evaluation).

Duration of overall complete response: The duration of overall CR is measured from the time measurement criteria are first met for CR until the first date that progressive disease is objectively documented, or death due to any cause. Participants without events reported are censored at the last disease evaluation.

Duration of stable disease: Stable disease is measured from the start of the treatment until the criteria for progression are met, taking as reference the smallest measurements recorded since the treatment started, including the baseline measurements.

11.1.6 Progression-Free Survival

Overall Survival: Overall Survival (OS) is defined as the time from randomization (or registration) to death due to any cause, or censored at date last known alive.

Progression-Free Survival: Progression-Free Survival (PFS) is defined as the time from randomization (or registration) to the earlier of progression or death due to any cause. Participants alive without disease progression are censored at date of last disease evaluation.

Time to Progression: Time to Progression (TTP) is defined as the time from randomization (or registration) to progression, or censored at date of last disease evaluation for those without progression reported.

12. DATA REPORTING / REGULATORY REQUIREMENTS

Adverse event lists, guidelines, and instructions for AE reporting can be found in Section 7.0 (Adverse Events: List and Reporting Requirements).

12.1 Data Reporting

12.1.1 Method

The ODQ will collect, manage, and perform quality checks on the data for this study.

12.1.2 Responsibility for Data Submission

Investigative sites within DF/HCC or DF/PCC are responsible for submitting data and/or data forms to the ODQ according to the schedule set by the ODQ.

12.2 Data Safety Monitoring

The DF/HCC Data and Safety Monitoring Board (DSMB) will review and monitor study progress, toxicity, safety and other data from this study. The board is chaired by a medical oncologist from outside of DF/HCC and has external and internal representation. Information that raises any questions about participant safety or protocol performance will be addressed by the Overall PI, statistician and study team. Should any major concerns arise, the DSMB will offer recommendations regarding whether or not to suspend the study.

The DSMB will meet twice a year to review accrual, toxicity, response and reporting information. Information to be provided to the DSMB may include: participant accrual; treatment regimen information; adverse events and serious adverse events reported by category;

summary of any deaths on study; audit results; and a summary provided by the study team. Other information (e.g. scans, laboratory values) will be provided upon request.

12.3 Multicenter Guidelines

This protocol will adhere to the policies and requirements of the DF/HCC Multi-Center Data and Safety Monitoring Plan. The specific responsibilities of the Overall PI, Coordinating Center, and Participating Institutions and the procedures for auditing are presented in Appendix E.

- The Overall PI/Coordinating Center is responsible for distributing all IND Action Letters or Safety Reports to all participating institutions for submission to their individual IRBs for action as required.
- Mechanisms will be in place to ensure quality assurance, protocol compliance, and adverse event reporting at each site.
- Except in very unusual circumstances, each participating institution will order the study agent(s) directly from supplier. A participating site may order the agent(s) only after the initial IRB approval for the site has been forwarded to the Coordinating Center.

12.4 Collaborative Research and Future Use of Data and Samples

Tissue, blood, stool, bodily fluids, and other materials derived from these will be collected in this study to analyze genes, DNA, RNA, proteins and cells for the study's correlative endpoints and potential future research, utilizing new types of biomarker testing as it becomes available.

These samples and any data generated as a part of these clinical trials may be used for future research studies and may be provided to collaborating investigators both within and outside of the DF/HCC for either correlative endpoints or secondary use. Samples and data may be shared with outside non-profit academic investigators, as well as with for-profit pharmaceutical investigators or commercial entities, with whom we collaborate. When samples or data are sent to collaborators and when any research is performed on them, all information will be identified with a code, and will not contain any PHI, such as name, birthday, or MRNs.

In order to allow the greatest amount of research to be performed on the specimens and information generated as a part of this trial, researchers in this study may share results of genetic sequencing with other scientists. De-identified specimen or genetic data may be placed into one of more publicly-accessible scientific databases, such as the National Institutes of Health's Database for Genotypes and Phenotypes (dbGaP). The results from the correlative research on this study will be shared with these public databases. Through such databases, researchers from around the world will have access to de-identified samples or data for future research. More detailed information, beyond the public database, may only be accessed by scientists at other research centers who have received special permission to review de-identified data.

13. STATISTICAL CONSIDERATIONS

13.1 Study Design/Endpoints

This is a randomized two-arm phase II study of neratinib +/- fulvestrant in patients with metastatic ER+/HER2+ breast cancer. The primary objective is to compare the progression-free survival between neratinib monotherapy versus neratinib plus fulvestrant. The endpoint is progression-free survival (PFS) defined as the interval from the date of randomization to progression or death. Patients who are alive and progression-free will be censored at the date of last disease assessment. Randomization will be 1:1 within stratum defined by the number of prior lines of therapy (≤ 3 versus ≥ 4) and prior use of fulvestrant (yes or no). Prior to Version 2 of the protocol, participants were stratified by the number of prior lines of therapy (≤ 3 versus ≥ 4) and PR expression (0-10% vs. 11% or more).

13.2 Sample Size, Accrual Rate and Study Duration

The total planned sample size is 152 patients (76 patients on each arm), which is calculated based on the number of randomized patients and defines the intention-to-treat population for efficacy analysis. The study is sized to have 82.3% power to detect improvement of median PFS from 4 months with neratinib monotherapy to 6 months with neratinib + fulvestrant (HR=0.67) using a stratified logrank test with a one-sided alpha level of 0.1, and final analysis to occur when 125 PFS events are observed. This assumes that the total planned sample size is enrolled at a constant accrual over 18 months with 6 months of additional follow-up, and a constant hazard of PFS and dropout such that 5% of patients are lost-to-follow-up at 1 year. One futility analysis is planned at 50% information (63 PFS events) and will stop early if the Z-statistic from the logrank test is less than 0 (i.e. observed HR from a Cox model > 1.0). No early stopping for efficacy will be considered. Power and sample size were calculated using East v6.4 (Cytel Inc., Cambridge MA).

We anticipate enrollment of approximately 8.5 patients per month. Patients will be followed for up to five years after removal from study or until death, whichever occurs first.

13.3 Stratification Factors

We will stratify patients based on two factors: number of prior lines of therapy (≤ 3 versus ≥ 4) and prior use of fulvestrant (yes or no).

13.4 Analysis of Primary Endpoints

The primary analysis of the study will be the comparison of PFS per RECIST 1.1 between neratinib monotherapy versus neratinib plus fulvestrant using a stratified logrank test with an overall one-sided Type I error rate at 0.1.

All inferences will be conducted in the intent-to-treat manner with all randomized patients

evaluated according to treatment assignment that was given, and the survival function will be summarized using the Kaplan-Meier methods according to randomized treatment assignment. Final analysis will be performed after 126 PFS events are observed or at least 12 months after the last patient is enrolled on study, whichever occurs first.

13.5 Analysis of Secondary Endpoints

- 13.5.1 We will estimate the clinical activity, as measured by overall survival (OS) of neratinib combined with fulvestrant compared with neratinib alone in patients with inoperable locally advanced or metastatic HER2-positive, ER-positive breast cancer. OS is defined as the length of time from randomization until death from any cause.
- 13.5.2 We will estimate the clinical activity, as measured by objective response rate (ORR) of neratinib combined with fulvestrant compared with neratinib alone in patients with inoperable locally advanced or metastatic HER2-positive, ER-positive breast cancer. ORR is defined as the proportion of patients with CR or PR according to RECIST v1.1.
- 13.5.3 We will estimate the clinical activity, as measured by duration of response (DoR), of neratinib combined with fulvestrant compared with neratinib alone in patients with inoperable locally advanced or metastatic HER2-positive, ER-positive breast cancer. DoR is defined as the time from the date of first evidence of CR or PR to the date of objective progression (according to RECIST v1.1) or death from any cause, whichever is earlier.

The hazard ratio for each secondary time-to-event endpoint will be estimated with 95% confidence intervals derived from the Cox proportional hazard model, but no hypothesis testing will be conducted. Objective response per RECIST 1.1 will be reported with 95% exact confidence intervals using a Pearson chi-squared test for difference in proportions with a one-sided alpha of 0.1.

13.6 Analysis of Correlative Endpoints

- 13.6.1 The proportion of patients with *ESR1* gene mutations, *PIK3CA* gene mutations, and loss of PTEN expression in baseline tumor tissue, and the proportion of patients with *PIK3CA* and *ESR1* gene mutations in circulating tumor DNA (ctDNA) from blood obtained at study baseline will be summarized using 95% binomial exact tests and exploratory analyses will characterize the association of molecular phenotypes with other patient and disease characteristics using Fisher exact tests.

13.6.2 The concordance of *PIK3CA* mutation status and *ESR1* mutation status assessed in circulating free tumor DNA and distant metastasis specimens (i.e. liquid and solid biopsies) will be assessed using kappa statistics with 95% confidence intervals obtained from bootstrap resampling. Operating characteristics including sensitivity, specificity, PPV and NPV will be used to summarize the performance of the liquid biopsy against solid biopsy as the ‘gold standard’. For any quantitative assessments of mutation status in the liquid biopsy, we will use ROC analysis to explore thresholds to optimize the linear combination of sensitivity and specificity (i.e. Youden index) for either absolute counts or estimates of the allele frequency. The following table provides the levels of precision in estimating sensitivity for varying failure rates of the paired assays and anticipated prevalence of 40% (*PIK3CA*) and 20% (*ESR1*) gene mutations.

Failure rate	Number of evaluable pairs	Maximum Width of CI for Sensitivity	
		40% prevalence	20% prevalence
10%	137	0.39	0.28
20%	122	0.41	0.29
30%	106	0.44	0.31

13.6.3 All other molecular characterization of potential resistance mechanisms, predictive biomarkers, and immunological function by collecting blood and tumor specimens will be exploratory and descriptive-only.

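### Section 13.6.2 picks ctDNA thresholds by the Youden index with no internal validation; accuracy quoted at that cut from the same pairs would be biased upward, by an amount that depends on the marker distribution

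*Combined protocol and SAP*

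**What the plan says.** Section 13.6.2 compares PIK3CA and ESR1 status in ctDNA with status in metastatic tissue, which serves as the reference. Agreement is measured by "kappa statistics with 95% confidence intervals obtained from bootstrap resampling". The plan continues: "Operating characteristics including sensitivity, specificity, PPV and NPV will be used to summarize the performance of the liquid biopsy against solid biopsy". A conditional sentence follows. It opens "For any quantitative assessments of mutation status in the liquid biopsy" and then says "we will use ROC analysis to explore thresholds to optimize the linear combination of sensitivity and specificity", naming the Youden index, with the search run on either absolute counts or allele-frequency estimates.

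A precision table for sensitivity follows, covering "varying failure rates of the paired assays" and "anticipated prevalence of 40% (*PIK3CA*) and 20% (*ESR1*) gene mutations". It lists 137, 122 and 106 evaluable pairs at failure rates of 10%, 20% and 30%.

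The section names no cut fixed in advance, no independent or split sample, no cross-validation and no optimism correction. The bootstrap is specified only for the kappa interval. Section 13.6.3 limits the remaining molecular work to exploratory description, but by its wording it covers work other than that in 13.6.2.

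**The concern.** A cut that maximises sensitivity plus specificity in a sample partly fits the noise of that sample. Scoring the cut on the same sample counts that noise as accuracy. The bias runs in one direction and grows as the mutation-positive group shrinks, so at equal discrimination ESR1 is affected more than PIK3CA.

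The plan describes no pairs other than the trial's own. Any accuracy figure quoted at the selected cut would therefore come from the data that selected it, unless the analyst adds a step that the plan does not mention. Liquid-solid concordance for both genes is a listed correlative objective (1.4.4 and 1.4.5), so these figures are likely to be read. The stake is a too favourable description of the ctDNA assay. The treatment comparison is not involved.

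**Working it through.** **Inputs.** From the documents: 152 patients (13.2); failure rates of 10%, 20% and 30%, and prevalences of 40% for PIK3CA and 20% for ESR1 (13.6.2). Assumed, because the documents do not give it: the distribution of the quantitative readout in mutation-positive and mutation-negative patients.

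**Step 1: the plan's own figures.** Pairs = 152 × (1 − failure rate) = 136.8, 121.6 and 106.4, which reproduces 137, 122 and 106. Positives = prevalence × pairs:
- 40%: 54.8, 48.8 and 42.4, about 55, 49 and 42.
- 20%: 27.4, 24.4 and 21.2, about 27, 24 and 21.

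The largest Clopper-Pearson 95% width over all possible counts is:
- 55, 49 and 42 positives: 0.28, 0.29 and 0.32.
- 27, 24–25 and 21 positives: 0.39, 0.41–0.42 and 0.44–0.45.

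The table prints 0.39, 0.41 and 0.44 under 40% prevalence and 0.28, 0.29 and 0.31 under 20%. The widths match to within about 0.01, but only with the two column headings exchanged. That labelling should be checked separately. For this point, what matters is that these are exact binomial widths for a fixed rule, with no allowance for threshold selection.

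**Step 2: optimism at the selected cut.** In each simulated data set the cut c* maximises empirical sensitivity plus specificity. Optimism is the mean of (empirical sensitivity at c*) − (true sensitivity at c*).
- Binormal readout: negatives N(0,1), positives N(δ,1), δ = √2·Φ⁻¹(AUC), true sensitivity 1 − Φ(c − δ). For AUC 0.7, 0.8 and 0.9, δ = 0.74, 1.19 and 1.81.
- Zero-inflated readout: zero unless mutant DNA is detected, a positive level otherwise, with stated detection and false-positive rates.

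Mean optimism in sensitivity, in percentage points:

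| Assumed readout | 20% prevalence (ESR1) | 40% prevalence (PIK3CA) |
|---|---|---|
| Binormal, AUC 0.7 | 8.2–9.5 | 4.9–5.5 |
| Binormal, AUC 0.8 | 7.5–8.3 | 4.3–4.8 |
| Binormal, AUC 0.9 | 5.9–7.0 | 3.6–3.9 |
| Unequal-variance binormal, AUC 0.85 | 6.3 (106 pairs) | 3.2 (137 pairs) |
| Zero-inflated, 70–90% detection, 5–20% false positives | 3.0–4.8 | 1.5–2.6 |
| Zero-inflated, 85% detection, 2% false positives | 2.0 (106 pairs) | 0.4 (137 pairs) |

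Ranges run from 137 to 106 pairs with 2,500 replicates per cell. The single-value entries used 300 replicates. Weaker discrimination raises the figures: at AUC 0.60 they are 9.2–10.7 and 5.5–6.9. At AUC 0.95 they fall to 5.1–6.0 and 2.9–3.4.

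Specificity is overstated by 1.1–4.2 points in the equal-variance binormal runs (AUC 0.60–0.95). PPV and NPV were not simulated. At a given prevalence both rise with sensitivity and specificity, so they move the same way.

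**Step 3: does a correction work?** In a separate set of runs (300 data sets per scenario, Monte Carlo standard error about 0.3–0.55 points), uncorrected optimism ranged from 0.4 to 9.8 points. Re-selecting the cut inside 10-fold cross-validation left −1.2 to +1.2 points. Bootstrap optimism correction left −0.2 to +3.7 points. Uncorrected exact 95% intervals at the selected cut covered the true sensitivity in 91% to 97% of data sets.

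**The case against.** The strongest reply is that the plan does not commit to the step that causes the bias. The ROC sentence applies only if a quantitative readout is used, and it speaks of exploring thresholds. The sentence on operating characteristics comes before it and can be read as referring to the assay's own mutation calls. Nothing says that sensitivity at the selected cut will be presented as the assay's performance. This stands, and it is why the point is worded conditionally. It does not dispose of the point: the plan does not exclude such reporting, and the exploratory label in 13.6.3 does not reach 13.6.2.

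A second reply is that the effect is small beside the plan's own interval widths of 0.28 to 0.44, and that exact intervals still cover reasonably well. That also stands, and it keeps the point minor. But imprecision does not excuse a bias that runs in one direction and can be largely removed at almost no cost.

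A reader might infer that the plan overstates sensitivity by a definite 4 to 10 points. The documents do not support that. They give no AUC, marker distribution or expected sensitivity, and counts or allele fractions with many zeros give mostly smaller values. A reader might also infer that the optimised figures are meant to justify using ctDNA in place of tissue. The documents do not say so. They set out to determine concordance and, in section 2.5.1, to examine the usefulness of ctDNA for following molecular change over time. No eligibility or treatment rule depends on a ctDNA cut.

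**Conclusion.** The concern holds in conditional form, as a minor point. If a quantitative ctDNA readout is used, and if accuracy is reported at a Youden-selected cut from the same 106 to 137 pairs, that accuracy is biased upward.

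Under an equal-variance binormal marker with AUC 0.7 to 0.9, the overstatement of sensitivity is about 6 to 10 points for ESR1 and 4 to 6 for PIK3CA. Under zero-inflated readouts it is about 1.5 to 5 points, and 0.4 to 2 with very clean separation. The direction was the same in every scenario. The size rests wholly on the assumed distributions and on the plan's prevalences, and the difference between the genes also assumes equal discrimination. The primary PFS comparison is not touched.

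**What to change.** Add to 13.6.2 that any cut derived from the trial data is exploratory. Sensitivity, specificity, PPV and NPV at that cut should be reported with the whole search, including any choice between counts and allele frequency, repeated inside each cross-validation fold. Repeating it inside bootstrap resamples is acceptable, but in the runs above it left up to about 4 points of bias, against about −1 to +1 for cross-validation. Intervals should reflect threshold selection. Extending the kappa bootstrap would be a new specification, since the plan provides "95% confidence intervals obtained from bootstrap resampling" for kappa alone. Fixing the cut before the paired data are seen would also remove the problem.

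The cost is a few lines of code and slightly less favourable reported accuracy. No new data are needed.

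### The two prevalence columns in the ctDNA sensitivity precision table (Section 13.6.2) are exchanged, so ESR1 is credited with the precision that belongs to PIK3CA

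*Combined protocol and SAP*

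**What the plan says.** Section 13.6.2 (Analysis of Correlative Endpoints) plans to compare PIK3CA and ESR1 mutation status between ctDNA and metastatic tissue. Besides kappa, it will use sensitivity, specificity, PPV and NPV to "summarize the performance of the liquid biopsy against solid biopsy as the" gold standard. It then states: "The following table provides the levels of precision in estimating sensitivity for varying failure rates of the paired assays", with an "anticipated prevalence of 40% (*PIK3CA*) and 20% (*ESR1*) gene mutations".

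The table gives three assay failure rates with their evaluable pairs, and under the heading "Maximum Width of CI for Sensitivity" two columns in the order "40% prevalence 20% prevalence". The first two rows read "10% 137 0.39 0.28" and "20% 122 0.41 0.29". The third row, for 30% failure, has 106 pairs with 0.44 under 40% prevalence and 0.31 under 20% prevalence.

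**The concern.** With tissue as the reference standard, the denominator for sensitivity is the number of tissue-positive pairs, which is the number of evaluable pairs times the prevalence. For a given number of pairs, 20% prevalence leaves half the positives that 40% leaves, so its interval has to be the wider of the two. The table shows the opposite in every row.

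Concordance of liquid and solid biopsy is a named correlative objective for each gene (Sections 1.4.4 and 1.4.5), and this table holds the only precision figures that the plan offers for that comparison. As printed, it presents the comparison with fewer informative patients (ESR1) as the more precise one.

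**Working it through.** **Inputs from the plan**

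- Planned sample size: 152 (Section 13.2).
- Assay failure rates: 10%, 20% and 30% (table in Section 13.6.2).
- Prevalence: 40% for PIK3CA and 20% for ESR1 (Section 13.6.2).
- Tabulated quantity: the maximum width, that is, the largest width over all possible observed counts.

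**Assumptions.** The plan does not give a confidence level or a method for the sensitivity interval. I take 95% exact binomial (Clopper-Pearson) because Section 13.6.1 names 95% and exact binomial methods for the mutation proportions. I round the number of positives up.

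**Step 1: evaluable pairs.** Pairs = 152 × (1 − failure rate):

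- 152 × 0.9 = 136.8, so 137
- 152 × 0.8 = 121.6, so 122
- 152 × 0.7 = 106.4, so 106

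These agree with the printed table.

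**Step 2: tissue-positive pairs.** m = pairs × prevalence:

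- At 40%: 54.8, 48.8 and 42.4, rounded up to 55, 49 and 43
- At 20%: 27.4, 24.4 and 21.2, rounded up to 28, 25 and 22

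**Step 3: maximum width.** For x detected among m positives, the lower limit is the 0.025 quantile of Beta(x, m − x + 1) and the upper limit is the 0.975 quantile of Beta(x + 1, m − x). I take the largest difference over x = 0 to m, which occurs at x close to m/2. For example, with m = 28 the maximum is at x = 14, with limits 0.3065 and 0.6935 and width 0.387.

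| Pairs | Prevalence | Positives | Computed maximum width | Printed under this prevalence | Printed under the other prevalence |
|---|---|---|---|---|---|
| 137 | 40% | 55 | 0.276 | 0.39 | 0.28 |
| 122 | 40% | 49 | 0.292 | 0.41 | 0.29 |
| 106 | 40% | 43 | 0.312 | 0.44 | 0.31 |
| 137 | 20% | 28 | 0.387 | 0.28 | 0.39 |
| 122 | 20% | 25 | 0.409 | 0.29 | 0.41 |
| 106 | 20% | 22 | 0.436 | 0.31 | 0.44 |

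No cell reproduces under its printed label. All six reproduce to two decimals under the other label.

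**Step 4: could another formula explain the printed labels?** At 137 pairs:

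| Method | 40% prevalence (printed 0.39) | 20% prevalence (printed 0.28) |
|---|---|---|
| Wald at p = 0.5, 95% | 0.264 | 0.370 |
| Wilson, 95% | 0.256 | 0.347 |
| Exact, 90% | 0.236 | 0.334 |
| Exact, 80% | 0.188 | 0.270 |
| Exact, 95%, tissue-negative denominator | 0.224 (83 negatives) | 0.194 (110 negatives) |

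The 80% exact interval comes close to 0.28 at 20% prevalence, but it then gives 0.19 at 40%, not 0.39. The last row shows that this is not a specificity table under the wrong title. None of these alternatives fits the printed labels.

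**Step 5: effect of rounding.** Rounding positives to the nearest integer gives 55, 49 and 42 (0.276, 0.292, 0.316) and 27, 24 and 21 (0.394, 0.418, 0.445). No cell moves by more than about 0.01. Rounding up is the convention that matches the printed figures in all six cells.

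**Step 6: size of the error,** using the two-decimal figures. For ESR1 the width is understated by 0.39 − 0.28 = 0.11, 0.41 − 0.29 = 0.12 and 0.44 − 0.31 = 0.13. Relative to the correct width this is 0.11/0.39 = 28%, 0.12/0.41 = 29% and 0.13/0.44 = 30%. For PIK3CA the width is overstated by the same 0.11, 0.12 and 0.13.

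**The case against.** The case for leaving this alone is mainly about consequence. The table supports correlative endpoints only. The figure of 152 patients comes from the PFS power calculation, no test or stopping rule uses these widths, and the plan sets no threshold for adequate precision. The final report will use the observed counts, so a mislabelled planning table cannot bias a result. Concordance itself is to be assessed by kappa with bootstrap intervals, for which the table gives no precision at all. All of this stands and limits the weight of the point.

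A second objection is that the size of the error, unlike its direction, depends on an unstated method. With 28 positives the 95% width is 0.387 by the exact method, 0.370 by Wald and 0.347 by Wilson. This is fair, but the six-cell match is strong evidence that the exact method was the one used.

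Third, these are worst-case widths, reached at a sensitivity near 0.5. At an observed sensitivity of about 0.9, exact 95% intervals with 21 to 28 positives are about 0.26 to 0.29 wide. That is true, but the table says that it reports the maximum, and the same reduction applies to the 40% column.

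Fourth, the column order might be an artefact of text extraction. The sentence before the table also lists 40% first and 20% second, so this is unlikely; a look at the header in the source PDF would settle it.

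**Conclusion.** The concern holds. The direction of the error follows from the definition of sensitivity and needs no assumption about the interval method. The size rests on two assumptions, 95% exact intervals and positives rounded up, and under these the whole printed table is recovered with its columns exchanged. This is a transposition, not a different calculation.

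On the plan's own inputs, the worst-case width for ESR1 sensitivity is 0.39 to 0.44, from about 21 to 28 tissue-positive pairs, not 0.28 to 0.31. For PIK3CA it is 0.28 to 0.31, not 0.39 to 0.44. The correction should be made because the stated precision of a named correlative analysis is wrong. It does not touch the PFS comparison, the sample size or any planned analysis method.

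**What to change.** Exchange the contents of the two columns in the Section 13.6.2 table and add the number of tissue-positive pairs:

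| Failure rate | Evaluable pairs | 40% prevalence (PIK3CA): positives, maximum width | 20% prevalence (ESR1): positives, maximum width |
|---|---|---|---|
| 10% | 137 | 55, 0.28 | 28, 0.39 |
| 20% | 122 | 49, 0.29 | 25, 0.41 |
| 30% | 106 | 43, 0.31 | 22, 0.44 |

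Add a note that gives the confidence level, the interval method and the rounding rule (95% exact and rounding up, if the sponsor confirms these were used), and that the maximum arises at a sensitivity near 0.5.

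The cost is one table edit and a footnote. The stated precision for ESR1 becomes less favourable and that for PIK3CA more favourable; nothing else in the plan changes.
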